### **8.3.2 Secondary Endpoint(s)**

The first secondary objective will be measured by the DOR based on IRRC assessment. DOR is defined as the time from first remission (CR or PR) to the date of initial objectively documented progression as determined using the 2007 IWG criteria or death due to any cause, whichever occurs first. For subjects who neither progress nor die, the DOR will be censored on the date of their last evaluable tumor assessment. Subjects who start subsequent therapy without a prior reported progression will be censored at the last evaluable tumor assessments prior to initiation of the subsequent anticancer therapy. This endpoint will only be evaluated in subjects with objective response of CR or PR.

[figure not shown]
The second secondary objective will be measured by the CRR based on IRRC assessment. The CRR is defined as the number of subjects with a BOR of CR according to the 2007 IWG criteria, divided by the number of treated subjects. The BOR is defined similarly as above. The duration of CR will only be evaluated in subjects with BOR of CR and is defined as the time from first documentation of CR (the date of first negative FDG-PET scan or the date of first documentation of no disease involvement in the bone marrow (if required), whichever occurs later) to the date of initial objectively documented progression as determined using the revised 2007 IWG criteria for malignant lymphoma or death due to any cause, whichever occurs first. Censoring will be applied as per DOR definition.

The third secondary objective will be measured by PR rate based on IRRC assessment. It is defined as the number of subjects with a BOR of PR according to the 2007 IWG criteria, based on IRRC assessment, divided by the number of treated subjects. The duration of PR will only be evaluated in subjects with BOR of PR and is defined as the time from first documentation of PR to the date of initial objectively documented progression as determined using the 2007 IWG criteria or death due to any cause, whichever occurs first. Censoring will be applied as per DOR definition.

The fourth secondary objective will be measured by IRRC-assessed PFS. It is defined as the time from first dosing date to the date of the first documented progression, as determined by an IRRC, or death due to any cause, whichever occurs first. Subjects who die without a reported progression will be considered to have progressed on the date of their death. Subjects who did not progress or die will be censored on the date of their last evaluable assessment. Subjects who did not have any on study assessments and did not die will be censored on the first dosing date. Subjects who started any subsequent anti-cancer therapy without a prior reported progression will be censored at the last evaluable assessment prior to initiation of the subsequent anti-cancer therapy.

The fifth secondary objective will be measured by investigator-assessed ORR. Investigator-assessed ORR is defined similarly as described for the primary endpoint above.

### **8.3.3 Exploratory Endpoint(s)**

## **8.4 Analyses**

### **8.4.1 Demographics and Baseline Characteristics**

Demographic and baseline laboratory results will be summarized using descriptive statistics for all treated subjects

### **8.4.2 Efficacy Analyses**

#### **8.4.2.1 Primary Endpoint Methods**

The IRRC-assessed ORR will be summarized by a binomial response rate and its corresponding two-sided 95% exact CI using the Clopper-Pearson method. The null hypothesis will be rejected if the 2-sided 95% CI lower bound is greater than 20%. This translates in observing at least 27 responders out of 90 treated subjects.

[figure not shown]
As sensitivity analysis, a summary of IRRC-assessed ORR based on response evaluable subjects instead of all treated subjects will also be presented.

#### **8.4.2.2 Secondary Endpoint Methods**

The IRRC-assessed DOR will be summarized for subjects who achieve PR or CR using the Kaplan-Meier (KM) product-limit method. Median value of DOR, along with two-sided 95% CI (based on the log-log transformation) and range, will also be calculated.

IRRC-assessed CRR, PRR and investigator-assessed ORR will be summarized similarly to the primary endpoint. Duration of CR and PR will be summarized similarly to DOR. IRRC-assessed PFS will be summarized descriptively using the KM product-limit method. Median value of PFS, along with two-sided 95% CI (based on the log-log transformation), will also be calculated.

### **8.4.2.3 Exploratory Endpoint Methods**

### **8.4.3 Safety Analyses**

Safety analyses will be performed in all treated subjects. Descriptive statistics of safety will be presented using NCI CTCAE version 4.0. All on-study AEs, drug-related AEs, SAEs, and drug-related SAEs will be tabulated using worst grade per NCI CTCAE v4.0 criteria by system organ class and MedDRA preferred term. On-study lab parameters including hematology, chemistry, liver function, thyroid function, and renal function will be summarized using worst grade per NCI CTCAE v4.0 criteria.

### **8.4.4 Pharmacokinetic Analyses**

The nivolumab concentration data obtained in this study may be combined with data from other studies in the clinical development program to develop or refine a population PK model. This model may be used to evaluate the effects of intrinsic and extrinsic covariates on the PK of nivolumab to determine measures of individual exposure (such as steady-state peak, trough, and time-averaged concentration). Model determined exposures may be used for exposure-response analyses. Results of population PK and exposure-response analyses will be reported separately.

### **8.4.5 Biomarker Analyses**

Methodology for exploratory biomarker analyses is described in the statistical analysis plan.

### **8.4.6 Outcomes Research Analyses**

The analysis of EORTC QLQ-C30 will be performed in all treated subjects who have an assessment at baseline (Visit 1 assessment prior to administration of drug) and at least 1 subsequent assessment.

All scales and single items are scored on categorical scales and linearly transformed to 0-to-100 scales with higher scores for a functional scale representing higher levels of functioning, higher scores for the global health status/quality of life representing higher levels of global health status/quality of life and higher scores for a symptom scale representing higher level of symptoms. Data will be analyzed as change from baseline scores. Baseline and change from baseline in EORTC QLQ-C30 global health status/QoL composite scale data and the remaining EORTC QLQ-C30 scale data will be summarized using descriptive statistics (N, mean, standard deviation, median, first and third quartiles, minimum, maximum) at each of the assessment time points. In addition, the percentage of subjects demonstrating a clinically

meaningful deterioration (defined as a 10 point change from baseline) will be presented for each scale at each assessment timepoint. Percentages will be based on number subjects assessed at assessment time point.

As previously mentioned in [Section 5.1](#), the EQ-5D comprises 5 dimensions (mobility, self-care, usual activities, pain/discomfort, and anxiety) and a VAS. EQ-5D data will be described in the following three ways:

- Subject's overall health state on a visual analog scale (EQ-VAS) at each assessment time point will be summarized using descriptive statistics. (N, mean, standard deviation, median, first and third quartiles, minimum, maximum).
- Proportion of subjects reporting problems for the 5 EQ-5D dimensions at each assessment time point will be summarized by level of problem. Percentages will be based on number subjects assessed at assessment time point
- A by-subject listing of EQ-5D with the problem levels for each of the 5 dimensions (mobility, self-care, usual activities, pain/discomfort and anxiety/depression), health state (5 dimensions digits combined in a 5-digit number) and EQ-VAS will be provided.

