## 8.2 Populations for Analyses

- All Enrolled Subjects: All subjects who signed an informed consent form and were registered into the IVRS
- All Treated Subjects: All subjects who received at least one dose of nivolumab. This is the primary population for safety and efficacy analyses
- All response evaluable subjects: All treated subjects who have baseline and at least one on-study evaluable tumor measurement
- PK subjects: All subjects with available serum time-concentration data from subjects dosed with nivolumab
- Immunogenicity evaluable subjects: all treated subjects with baseline and at least one post baseline immunogenicity assessment.
- All PD-L1 evaluable subjects: All treated PD-L1 subjects with quantifiable baseline PD-L1 expression
- Biomarker subjects: All treated subjects with available biomarker data
- Outcomes Research subjects: all treated subjects who have an assessment at baseline (Visit 1 assessment prior to administration of drug) and at least 1 subsequent assessment (for EORTC QLQ-C30 and EQ-5D separately).

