6.3 Populations for Analyses

6.3.1 Analysis Populations

The following populations will be defined.

- **All enrolled subjects:** All subjects who signed an informed consent form and were registered into the IVRS.
- **All treated subjects:** All enrolled subjects who received at least one dose of nivolumab. This is the primary population for efficacy and safety.
- **All response evaluable subjects:** All treated subjects who have baseline and at least one on-study evaluable tumor measurement.
- **PK subjects:** All enrolled subjects with available serum time-concentration data from subjects dosed with nivolumab.
- **Immunogenicity evaluable subjects:** all treated subjects with baseline and at least one post baseline immunogenicity assessment.
- **All PD-L1 tested subjects:** All enrolled subjects who had a tumor tissue sample available for assessment of PD-L1 expression.
- **All PD-L1 evaluable subjects:** All treated subjects with quantifiable baseline PD-L1 expression
- **Biomarker subjects:** All treated subjects with available biomarker data.
- **Outcomes Research subjects:** all treated subjects who have an assessment at baseline (Visit 1 assessment prior to administration of drug) and at least 1 subsequent assessment (for EORTC QLQ-C30 and EQ-5D separately).

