7.9 Outcome Research Analyses

7.9.1 EORTC-QLQ-C30 Questionnaire

Unless otherwise specified, the analysis of EORTC QLQ C-30 will be performed in all treated subjects who have an assessment at baseline and at least one subsequent assessment. Analyses will be performed.

Baseline measures will be summarized using descriptive statistics (N, mean, standard deviation, median, first and third quartiles, minimum, maximum) for each QLQ-C30 item, as well as global and functional scales, based on subjects with a baseline measurement.

Change from baseline will be summarized using descriptive statistics (N, mean, standard deviation, median, first and third quartiles, minimum, maximum) for each QLQ-C30 item, as well as global and functional scales at each assessment time point. In addition, the percentage of subjects demonstrating a clinically meaningful deterioration (defined as a 10 point change from baseline) will be presented for each scale at each assessment timepoint. Percentages will be based on number subjects assessed at baseline and at assessment time point.

EORTC-QLQ-C30 questionnaire completion rate, defined as the proportion of questionnaires actually received out of the expected number (i.e., number of subjects on treatment or in follow up), will be calculated and summarized for each assessment time point.

A by subject listing of QLQ-C30 with each QLQ-C30 item, functional scales and global health status will be provided.

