7.9.2 EQ-5D Questionnaire

Unless otherwise specified, the analysis of EQ-5D will be performed in all treated subjects who have an assessment at baseline and at least one subsequent assessment. Analyses will be performed.

Subject's overall health state on a visual analog scale (EQ-VAS) at each assessment time point will be summarized using descriptive statistics (N, mean, SD, median, 25th and 75th percentiles, minimum, maximum).

Proportion of subjects reporting problems for the 5 EQ-5D dimensions at each assessment time point will be summarized by level of problem. Percentages will be based on number subjects assessed at assessment time point.

A by-subject listing of EQ-5D with the problem levels for each of the 5 dimensions (mobility, self-care, usual activities, pain/discomfort and anxiety/depression), health state (5 dimensions digits combined in a 5-digit number) and EQ-VAS will be provided.

Results of EQ5D-Index will be presented separately and will be described in the GHEOR SAP.

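### EQ-VAS is summarised only as raw levels at each time point; adding change from baseline, as planned for QLQ-C30, would separate within-subject change from a shift in who is still assessed

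*Protocol*

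**What the plan says.** On EQ-5D, Protocol 8.4.6 says that "EQ-5D data will be described in the following three ways". The three are the EQ-VAS level at each time point, the proportion reporting each problem level on the five dimensions at each time point, and a by-subject listing. For EQ-VAS the wording is that the subject's "overall health state on a visual analog scale (EQ-VAS) at each assessment time point will be summarized using descriptive statistics"; SAP 7.9.2 uses the same words. For the dimension proportions, SAP 7.9.2 adds: "Percentages will be based on number subjects assessed at assessment time point".

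A baseline form is a condition of entry. SAP 7.9.2 states that "the analysis of EQ-5D will be performed in all treated subjects who have an assessment at baseline and at least one subsequent assessment". Protocol 8.2 and SAP 6.3.1 define the Outcomes Research population in the same way for each instrument.

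QLQ-C30 is handled differently. Protocol 8.4.6 says "Data will be analyzed as change from baseline scores", and SAP 7.9.1 says "Change from baseline will be summarized using descriptive statistics" at each time point.

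**The concern.** Protocol 5.7 gives assessing nivolumab's impact on generic quality of life as one purpose of collecting EQ-5D. In a single-arm trial the subject's own baseline is the only internal reference for impact, and no planned EQ-VAS summary makes that comparison. A reader of the planned table would compare the mean of everyone at baseline with the mean of whoever is still assessed later.

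The population rule fixes who enters the set, not who is assessed at each later visit. The set is likely to shrink over a long period: by Tables 5.1-2 and 5.1-3 of the protocol, EQ-5D runs from Cycle 1 Day 1 through treatment, two follow-up visits and then survival follow-up, whereas QLQ-C30 stops after the two follow-up visits. SAP 7.9.1 plans a completion rate for QLQ-C30; SAP 7.9.2 plans none for EQ-5D. What is at stake is how a trend in EQ-VAS would be read. No hypothesis or decision rule depends on it.

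**Working it through.** Neither document states an expected EQ-VAS mean, SD, change or retention, so there is no plan figure to reproduce. The check has a textual part and an illustrative part.

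**1. The texts side by side**

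- EQ-VAS (Protocol 8.4.6, SAP 7.9.2): N, mean, SD, median, quartiles, minimum and maximum of the level at each time point. No change, paired summary or longitudinal model.
- QLQ-C30 (Protocol 8.4.6, SAP 7.9.1): the same statistics for baseline and for change from baseline, plus the percentage deteriorating by 10 points.
- Deferred elsewhere: SAP 7.9.2 sends only the EQ-5D index to a separate plan, so that sentence does not promise an EQ-VAS change.

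The SAP therefore does not supply what the protocol leaves out.

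**2. Illustration of drift (all inputs assumed)**

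EQ-VAS = stable health level + measurement error. The level has mean 70 and SD 16; the error has SD 12. Total SD = √(16² + 12²) = 20, and the correlation between visits = 256/400 = 0.64. Nobody's level changes. The probability of still being assessed is p(z) = 1/(1 + exp(−a − s·z)), where z is the standardised level, s = 0.5 or 1.0, and a is set to give the stated retention. The expected raw mean at the visit is 70 + 16m, with m = E[Z·p(Z)]/E[p(Z)].

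| Retention | a (s = 0.5; 1.0) | m (s = 0.5; 1.0) | Rise in raw mean, 16m |
|---|---|---|---|
| 70% | 0.895; 1.018 | 0.143; 0.253 | 2.3; 4.0 |
| 50% | 0; 0 | 0.236; 0.413 | 3.8; 6.6 |
| 30% | −0.895; −1.018 | 0.333; 0.590 | 5.3; 9.4 |

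The baseline mean of the retained subjects is also 70 + 16m, so their mean change is 0.

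**3. A second selection rule**

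Now keep the top fraction f on a score that correlates r with baseline EQ-VAS, with change unrelated to staying. Drift = SD × r × λ, where λ = φ(Φ⁻¹(f))/f. For f = 80%, 60% and 40%, λ = 0.350, 0.644 and 0.966. With SD 15 to 25 and r = 0.3 to 0.5:

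- 80%: 15 × 0.3 × 0.350 = 1.6, to 25 × 0.5 × 0.350 = 4.4
- 60%: 2.9 to 8.0
- 40%: 4.3 to 12.1

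With r = 0 there is no drift. Mean change is 0 throughout.

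**4. Where pairing does not help**

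Suppose staying assessed correlates 0.3 with the change itself, and the change has SD 15. The raw mean and the paired mean are then shifted by the same amount, 15 × 0.3 × λ = 1.6, 2.9 and 4.3 points at 80%, 60% and 40% assessed.

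**The case against.** The strongest reply is that this is a consistent choice of descriptive display. The two documents agree with each other. Change in overall health is already covered by the QLQ-C30 global health scale, also scored 0 to 100 and analysed as change from baseline. EQ-5D serves largely to supply utilities for health economic models. N is reported for EQ-VAS at each time point, so shrinkage is visible, and every within-subject difference can be derived from the by-subject listing. The exploratory objectives are redacted, so no readable objective asks for EQ-VAS change. All of this stands and limits the weight of the point. It does not give the reader a planned paired summary.

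Three stronger readings are tempting, and the documents do not support them.

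- *The baseline score is never used.* It defines the analysis set, is collected at Cycle 1 Day 1 and so falls among the time points to be summarised, and appears in the listing. What is missing is a calculated change.
- *The raw display costs much precision.* Take, as assumptions, 85 baseline forms, 45 later forms and SD 20. Treating the two means as independent gives √(400/85 + 400/45) = 3.69, against 20 × √(2 × 0.36/45) = 2.53 for the paired change. But the 45 are among the 85, so 2 × 0.64 × 400/85 must be subtracted from the variance: √(4.71 + 8.89 − 6.02) = 2.75. Over correlations 0.75 to 0.4 the raw difference has standard error 2.6 to 3.1 and the paired change 2.1 to 3.3; at 0.4 pairing is slightly worse. Precision is not a reason for the change.
- *Pairing cures attrition bias.* Step 4 of the working shows that it does not.

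**Conclusion.** The point holds in a limited form. Both documents plan EQ-VAS only as levels among subjects assessed at each time point, while QLQ-C30 gets change from baseline in the same sections with no reason given for the difference. If staying on assessment depends on a stable health level, the raw mean can drift with no within-subject change: about 2 to 4 points at 70% retention, 4 to 7 at 50% and 5 to 9 at 30% under the first set of assumptions. The second rule gives a range of similar order.

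These are illustrations of a mechanism, not predictions. Every input is assumed. The drift vanishes if staying is unrelated to health level and reverses if less healthy subjects stay longer. The zero paired change follows from assuming that change is unrelated to staying. A reader might infer that the EQ-VAS results will be biased; the documents do not establish that, since they say nothing on who will stop being assessed or why. EQ-VAS is a descriptive measure and the ORR conclusion does not depend on it.

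**What to change.** In SAP 7.9.2, and in Protocol 8.4.6 if it is amended for other reasons:

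- Add EQ-VAS change from baseline at each time point among subjects with both values: N, mean, SD, median, quartiles, minimum and maximum, as for QLQ-C30.
- Beside it, show the baseline mean of those same subjects, so that a shift in who is assessed can be seen directly. Keep the raw levels.
- State that the paired summary does not remove bias if dropout depends on the change itself.

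Confidence intervals for the change and baseline-by-visit shift tables for the five dimensions are optional. The plan has no confidence intervals for QLQ-C30 change either, and shift tables at every visit would add considerably more output.

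The cost is a few sentences in the SAP and a few more rows per time point. All the data are already collected.

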#### **8.4.7 Other Analyses**

##### **8.4.7.1 Immunogenicity Analyses**

Immunogenicity may be reported for ADA positive status (such as persistent positive, neutralizing positive, only last sample positive, baseline positive) and ADA negative status, relative to baseline. Effect of immunogenicity on safety, efficacy, biomarkers and PK may be explored. Additional details will be described in the SAP.

#### **8.5 Interim Analyses**

Not applicable.

### **9 STUDY MANAGEMENT**

#### **9.1 Compliance**

##### **9.1.1 Compliance with the Protocol and Protocol Revisions**

The study shall be conducted as described in this approved protocol. All revisions to the protocol must be discussed with, and be prepared by, BMS. The investigator should not implement any deviation or change to the protocol without prior review and documented approval/favorable opinion from the IRB/IEC of an amendment, except where necessary to eliminate an immediate hazard(s) to study subjects.

If a deviation or change to a protocol is implemented to eliminate an immediate hazard(s) prior to obtaining IRB/IEC approval/favorable opinion, as soon as possible the deviation or change will be submitted to:

- IRB/IEC for review and approval/favorable opinion
- BMS
- Regulatory Authority(ies), if required by local regulations

Documentation of approval signed by the chairperson or designee of the IRB(s)/IEC(s) must be sent to BMS.

If an amendment substantially alters the study design or increases the potential risk to the subject: (1) the consent form must be revised and submitted to the IRB(s)/IEC(s) for review and approval/favorable opinion; (2) the revised form must be used to obtain consent from subjects currently enrolled in the study if they are affected by the amendment; and (3) the new form must be used to obtain consent from new subjects prior to enrollment.

If the revision is done via an administrative letter, investigators must inform their IRB(s)/IEC(s).

### **9.1.2 Monitoring**

Representatives of BMS must be allowed to visit all study site locations periodically to assess the data quality and study integrity. On site they will review study records and directly compare them with source documents, discuss the conduct of the study with the investigator, and verify that the facilities remain acceptable.

In addition, the study may be evaluated by BMS internal auditors and government inspectors who must be allowed access to CRFs, source documents, other study files, and study facilities. BMS audit reports will be kept confidential.

The investigator must notify BMS promptly of any inspections scheduled by regulatory authorities, and promptly forward copies of inspection reports to BMS.

### **9.1.3 Investigational Site Training**

Bristol-Myers Squibb will provide quality investigational staff training prior to study initiation. Training topics will include but are not limited to: GCP, AE reporting, study details and procedure, electronic CRFs, study documentation, informed consent, and enrollment of WOCBP.

